9.4.8.2. Clinical Laboratory Evaluation

Clinical laboratory values will be evaluated for each laboratory parameter by subject. Abnormal laboratory values will be identified as those outside (above or below) the normal range. Reference (normal) ranges for laboratory parameters will be included in the Clinical Study Report for this protocol.

Descriptive summary statistics (mean, standard deviation, median and range) of the laboratory parameters will be evaluated for hematology and biochemistry. Categorical values will be summarized using number of observations and percentages (urinalysis assessment).

Laboratory test results will be assigned an LNH classification according to whether the value was below (L), within (N), or above (H) the laboratory reference range. Summary data of LNH will be provided by the worst category and by the shift from baseline to the worst. In addition, the CTCAE grading system will be implemented to safety laboratory values. The resulted grades of laboratory assessments will be summarized as categorical data.

Clinical laboratory results will also be evaluated using outlier criteria (potentially clinically important per investigator's discretion). For the incidence of outliers, each patient will be counted only once in the laboratory parameter value high and low categories, as applicable.

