8.14.6. Clinical Laboratory Evaluations

A clinical laboratory AE is any laboratory value that is considered clinically significant by the Investigator and has caused a medical intervention or accompanied by clinical symptoms. Laboratory abnormalities that have not required medical intervention should not be recorded as AEs and will be captured and reported in the Laboratory section of the clinical study report. If a medical intervention occurs, it should be recorded as a treatment with the abnormal laboratory finding as the AE.

The Investigator should decide, based upon the AE criteria and the clinical condition of the patient, whether a change in a laboratory parameter is clinically significant and therefore represents an AE.

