9.1.1. Safety Endpoints

The following safety endpoints will be assessed:

- Incidence and severity of treatment-emergent adverse events;
- Incidence and severity of treatment-emergent changes in clinical laboratory values;
- Incidence of dose limiting toxicities;
- Incidence of anti-drug antibodies to JTX-2011 and/or nivolumab, ipilimumab, or pembrolizumab;
- Incidence of neutralizing antibodies to JTX-2011 and/or nivolumab, ipilimumab, or pembrolizumab;
- Incidence of decreases in ECOG performance status;
- Incidence of clinically significant changes in ECG measurements.

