#### 9.9.2 LABORATORY DATA

Laboratory parameters will be analyzed using categorical summaries.

Categorical analysis of laboratory tests using observed data includes summarizing laboratory abnormalities considered clinically significant and treatment-emergent. The following defines this group;

- Abnormality satisfies current criteria and occurs first time while the patient is on study treatment (i.e., not seen prior to treatment).
- Abnormality satisfies the current criteria of abnormality, was observed prior to start of treatment, and worsened during study treatment.

The number of patients evaluable for laboratory abnormalities must have at least one observation for at least one test while on treatment. While the number of patients evaluable for clinically significant laboratory abnormalities (includes lab TEAEs) is the number of patients with a clinically significant abnormality for at least one laboratory test while on treatment.

Additional summaries will be produced overall by Maximum CTCAE grade. Frequencies and percentages in each grade and overall will be presented.

Shift in laboratory analyte grade will be characterized by worst on-study CTCAE grade to end of treatment. Shift categories from baseline will be selecting the maximum CTCAE grade for each patient during the study compared to baseline. Grades that are not part of CTCAE grading will be blank. Percentages will be based on the number of patients with non-missing baseline and postbaseline values per each analyte.

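### SAP 9.9.2 omits the low/normal/high worst-category and shift tables promised in Protocol 9.4.8.2, so any analyte without a CTCAE grade has no shift table

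*Protocol*

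**What the plan says.** Protocol 9.1.1 names as a safety endpoint "Incidence and severity of treatment-emergent changes in clinical laboratory values". Protocol 9.4.8.2 sets out how it is to be reported. Results are "assigned an LNH classification according to whether the value was below (L), within (N), or above (H) the laboratory reference range", and "Summary data of LNH will be provided by the worst category and by the shift from baseline to the worst". Grading is an extra layer: "In addition, the CTCAE grading system will be implemented to safety laboratory values". The same section also plans descriptive statistics for hematology and biochemistry, and an incidence of outliers at the investigator's discretion.

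SAP 9.9.2 opens with "Laboratory parameters will be analyzed using categorical summaries". It then plans a summary of abnormalities that are clinically significant and treatment-emergent, a summary by maximum CTCAE grade, and a shift table: "Shift categories from baseline will be selecting the maximum CTCAE grade for each patient during the study compared to baseline". It adds: "Grades that are not part of CTCAE grading will be blank". The SAP mentions no L/N/H class, worst L/N/H category or L/N/H shift, and it does not record that these were removed.

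On what reaches the adverse event tables, Protocol 8.14.6 says: "Laboratory abnormalities that have not required medical intervention should not be recorded as AEs and will be captured and reported in the Laboratory section".

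**The concern.** The protocol gives every analyte with a reference range a simple, objective summary: how many subjects went out of range, and from what starting class. CTCAE grading was to supplement that summary. The SAP keeps the supplement and leaves out the base. An analyte that CTCAE does not grade then loses its only shift table. Its abnormalities are counted only where someone has judged them clinically significant.

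Safety is a primary objective of every part of the study, and Protocol 8.14.6 keeps untreated abnormalities out of the adverse event record on the footing that the laboratory section will report them. If the laboratory section has no objective count for an analyte, that arrangement fails for it. The thyroid panel shows why this could matter. Protocol 8.16.3 lists thyroid dysfunction as an expected immune-related event, and thyroid function is measured on Day 1 of every cycle (Protocol 7.2.1, 7.2.7, 7.2.9).

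**Working it through.** **Step 1: the two sections side by side.**

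| Element | Protocol 9.4.8.2 | SAP 9.9.2 |
|---|---|---|
| L/N/H class | Yes | Absent |
| Worst L/N/H category | Yes | Absent |
| L/N/H shift, baseline to worst | Yes | Absent |
| CTCAE grade summary | Yes, as an addition | Yes, maximum grade |
| CTCAE shift from baseline | Not specified | Yes |
| Values of potential clinical importance | Outliers at investigator's discretion, with high and low counted | Clinically significant, treatment-emergent abnormalities; criteria undefined |
| Descriptive statistics | Hematology and biochemistry | None in this section (SAP 7.2 has a general rule for continuous variables) |

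The SAP does explain another dropped item: SAP 3.2.4.2 and 9.11.7 say JTXP will not be analysed because of sample quality. No such statement is made for L/N/H. The inputs exist, because SAP 7.8.2 already compares laboratory values with the limits of normal.

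**Step 2: follow one result.** Take an out-of-range value in an analyte with no CTCAE grade, where no treatment was given.

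- Maximum-grade summary and CTCAE shift: blank.
- Clinically significant summary: counted only if judged clinically significant. The section refers to current criteria without stating them. Its evaluable count for this summary is the number of patients who have such an abnormality, so it cannot be the denominator of a rate.
- Adverse event tables: Protocol 8.14.6 keeps it out if no intervention was required. Protocol 8.8 would record it if the investigator judged it clinically significant.
- Otherwise it is in no count and no shift, and can be identified only in the listings.

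**Step 3: how many analytes.** Protocol Table 6 lists 20 chemistry, 11 hematology, 3 coagulation and 3 thyroid analytes: 20 + 11 + 3 + 3 = 37. The documents link to CTCAE v4.03 but do not reproduce it, so the number ungraded has to be assumed.

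- Thyroid tests only: 3/37 = 8.1%.
- Wider assumed set (thyroid 3, chloride, bicarbonate, total protein, BUN, LDH, direct and indirect bilirubin, RBC, hematocrit, monocytes, eosinophils, basophils, PT): 16/37 = 43.2%.

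Neither figure is established by the documents.

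**Step 4: what it would look like in one cohort.** In a 15-subject cohort, suppose 3 subjects move from normal to high TSH. Suppose also that TSH is ungraded, and that the changes are neither judged clinically significant nor recorded as adverse events. The protocol's shift table would show 3/15 = 20%. The SAP tables would count none of them.

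**Step 5: direction.** The CTCAE shift takes one maximum grade per patient, and the SAP does not say whether high and low grades are kept apart. If they are merged, a subject who goes from Grade 2 high at baseline to Grade 2 low on treatment is shown as 2 to 2, that is, no shift.

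**The case against.** There are four readings that a reader might infer and that the documents do not support.

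- *Untreated abnormalities in ungraded analytes appear in no abnormality table.* This is too broad. The clinically significant summary in SAP 9.9.2 requires neither a CTCAE grade nor treatment, and it is stated to include laboratory adverse events. Only values not judged clinically significant and not recorded as adverse events are missed.
- *The baseline-to-worst shift has been dropped.* It survives on the CTCAE scale. Only the L/N/H version is gone.
- *The thyroid panel is unreported.* Whether it is ungraded cannot be read from the documents. The SAP's sentence on blanks speaks of grades, and could mean grade levels that CTCAE does not define for an analyte. Thyroid events recorded as adverse events are tabulated, and SAP 8.1.1 evaluates hypothyroidism and hyperthyroidism as immune-related events, at a minimum in the combination arms.
- *The protocol's L/N/H rule counts high and low separately.* That wording belongs to its outlier sentence. The L/N/H sentence asks only for the worst category and the shift to worst.

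The general defence is that Protocol 9.4 calls its section high-level and leaves detail to the SAP, that Protocol 9.5.2 has changes documented in the study report, and that all laboratory data are still displayed (SAP 7.8.1). SAP 7.2 may also yield descriptive statistics, although SAP 9.9.2 speaks only of categorical summaries. Merging of directions is likewise not stated; table layouts are left to mock shells.

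These points limit the reach of the concern. They do not remove it: a specific table was promised, it is absent, and nothing records the change. Listings and means do not give an incidence or a shift.

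**Conclusion.** The point holds in this limited form: the L/N/H worst-category and shift tables are missing from SAP 9.9.2 without explanation. Followed as written, the SAP does not fully deliver the laboratory endpoint in Protocol 9.1.1.

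The consequence is conditional. It falls on analytes without a CTCAE grade, and within those on out-of-range values that are neither judged clinically significant nor recorded as adverse events. The 3 of 37 and 16 of 37 figures, and the 20% cohort example, are illustrations that rest on assumptions about CTCAE content. The documents themselves fix no number, and they do not establish that the thyroid tests are among those affected. The loss of direction in the CTCAE shift is a risk left open by the SAP's silence.

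No hypothesis test is affected. The effect is on the completeness of descriptive safety reporting. The change should be made because the protocol already promises the tables and they are cheap to produce.

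**What to change.** In SAP 9.9.2, restore the L/N/H classification for every Table 6 analyte with a reference range. Tabulate the worst post-baseline category and the shift from baseline to worst, out of subjects with a baseline and at least one post-baseline value. If the sponsor prefers to leave these tables out, the SAP should say so and give the reason.

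Two refinements go beyond the protocol's wording and are worth making. Show worst Low and worst High separately, so that a subject who goes out of range in both directions is not reduced to one category. For analytes that CTCAE grades in both directions, show maximum grade and shift by direction. The section should also state its criteria for a clinically significant abnormality and give that summary a usable denominator.

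The cost is a change of SAP wording and a few extra standard tables, from values and reference ranges already collected.

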9.4.8.3. Vital Signs

Vital sign values (BP, T, HR, RR, and SpO₂), and weight will be evaluated on an individual basis by patient. Abnormal vital sign values will be identified as those outside (above or below) the reference range. Descriptive summary statistics (mean, standard deviation, median, and range) for vital sign parameters will be tabulated.

9.5. Efficacy Analyses

For Parts C, D, F, and H, the rate of overall response (CR + PR), rate of disease control (CR+PR+SD), as well as rate of complete response, partial response, or stable disease will be summarized by frequencies and percentages for each cohort. The duration of response measured by the number of months from first confirmed CR/PR to disease progression will also be provided by cohort. The evaluation of the response will be based on RECIST v1.1 criteria and immune-related response criteria, respectively.

Time-to-progression free survival and overall survival will be estimated by Kaplan-Meier method. The median time to event will be presented with 25%- and 75%-quantiles.

More details of safety and efficacy analyses will be specified in SAP including the efficacy analyses for cohorts in Part A and B where efficacy is an exploratory endpoint.

As part of the exploratory objectives, the correlation between efficacy and potential predictive biomarkers will be evaluated to generate hypotheses for further testing and the details will be specified in EAP.

9.5.1. Interim Analyses

This is an open-label study. No formal interim analyses are planned within the current protocol. However, if the number of responses in any cohort of Parts C, D, or F is more than the prespecified futility boundary based on the group sequential design (Section 9.3), the study may enroll additional subjects for a more robust determination of efficacy.

9.5.2. Changes to the Planned Statistical Methods

Changes to the planned statistical methods will be documented in the clinical study report.

9.5.3. Pharmacokinetic Analyses

Pharmacokinetic parameters following the first dose will be calculated by non-compartmental analysis using validated software such as Phoenix WinNonLin v. 6.3 (Certara, Inc.). C_{max} and C_{min} values from subsequent doses will also be tabulated and reported. Only concentration values within the validated concentration range and actual sampling times will be used for the calculation of pharmacokinetic parameters. Concentrations used in the pharmacokinetic calculations will be in the same format provided in the bioanalytical report, (that is, to the same number of decimal places provided in the bioanalytical report).

If any pre-first dose value is greater than 5% of C_{max}, the subject's pharmacokinetic data will be not included in any statistical evaluations. The individual pharmacokinetic parameters of such a subject will be calculated and listed separately. If a pre-first dose concentration is above the lower limit of assay quantitation, but less than or equal to 5% of the subject's C_{max} value, the

subject's data will be included without any adjustments in all pharmacokinetic measurements and calculations.

Every effort will be made to include all concentration data in an analysis. If not possible, a case-by-case decision will be used to determine whether the value should only be excluded from half-life estimation or the complete analysis. If a concentration is only excluded from half-life determination, it will be used for all other calculations (e.g. descriptive statistics) and for graphical presentation.

The following descriptive statistics will be calculated for serum concentrations as well as for all pharmacokinetic parameters: N, arithmetic mean, standard deviation, minimum, median, maximum, arithmetic coefficient of variation, geometric mean, and geometric coefficient of variation. The data format for descriptive statistics of concentrations will be identical with the data format of the respective concentrations.

In tabulation of PK or PD data, scheduled samples that could not be obtained or analyzed, or samples from which concentration data was identified by the bioanalytical lab as below the limit of quantitation (BLQ) will be ignored and not replaced by zero at any time point except the pre-first dose baseline for PK. Descriptive statistics of concentrations or biomarkers at specific time points will be calculated only when at least $\frac{1}{2}$ of the individuals have concentrations or biomarker data within validated ranges. The overall sample size to decide whether the " $\frac{1}{2}$ rule" is fulfilled will be based on the total number of samples intended to be drawn for that time point.

Dose proportionality of the pharmacokinetic endpoints AUC_{0-tz} , $AUC_{0-\infty}$, and t_{ma} will be explored based on a standard regression model. Based on the estimate for the slope parameter β , a two-sided-95% confidence interval for the slope will be computed. The assumption of a linear relationship between the log-transformed pharmacokinetic endpoint and the log-transformed dose will be checked. Perfect dose proportionality would correspond to a slope of 1.

If dose proportionality over the entire dose range investigated cannot be shown, an attempt will be made to identify dose range(s) where dose proportionality can be assumed.

Attainment of steady state will be explored by pairwise comparison of the trough concentrations of JTX-2011 measured at the beginning of each treatment cycle. If trough concentrations cannot be reported because they are BLQ, attainment of steady state will be assessed from a population PK model.

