### 7.12.2 HANDLING OF MISSING AND NON-QUANTIFIABLE DATA FOR PHARMACOKINETIC ANALYSES

Concentration data will be considered missing if:

- No sample is collected
- A sample is collected but no valid bioanalytical data are reported for any reason

Missing values will be considered missing for the purposes of listing, summarization and analysis, with the exception that Cycle 1 Day 1 pre-dose concentrations will be set to “0” if missing for the purposes of NCA analysis.

If a sample is collected and analysed, but is of questionable identity due to possible sample handling or labelling errors either at the clinical site or the bioanalytical lab, the concentration will be reported and flagged in the listings, and the rationale for considering the identity questionable will be documented. The data will be set as missing in the primary NCA analysis and statistical summarization, but a sensitivity analysis may be conducted in which the concentration data point is included in the NCA and statistical summarization for NCA results for the relevant Dose and Cycle repeated.

If a quantifiable concentration is available but the actual sampling time is missing, the nominal sampling time will be used.

Bioanalytical data that are below the limit of quantitation (BLQ) will be treated as follows:

- For listings, BLQ will be reported as “< LLQ” (lower limit of quantitation)
- For NCA, BLQ concentrations will be set to 0

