## **9.10 PHARMACOKINETIC AND IMMUNOGENICITY ANALYSES**

### **9.10.1 PHARMACOKINETIC ANALYSES**

The PK analyses will be based on the PK analysis set, unless otherwise specified.

Plasma concentration data for JTX-2011 will be listed by subject and summarized in tables with standard descriptive statistics by analyte (Drug, i.e., JTX-2011, nivolumab, ipilimumab or pembrolizumab), Part, Dose Level, Cycle, and Time Point. Linear and log-linear plots of concentration versus time will be provided for individual subjects and for means by Drug, Part, Treatment (monotherapy or combination with nivolumab, ipilimumab, pembrolizumab), Dose Level, and Cycle.

PK parameters will be determined by NCA using a validated software platform (WinNonlin/Phoenix™ version 8.0 or higher). Actual sampling times will be used and the estimation method will be linear up, linear down. The analysis will be conducted by or under the oversight of the Clinical Pharmacologist at Jounce. Derived PK parameters will be provided to the statistical department at Jounce to be listed by subject and summarized in tables by Drug, Part, Treatment, Dose Level, and Cycle with descriptive statistics (n, mean, standard deviation, median, minimum, maximum and, for  $C_{max}$  and AUC parameters, geometric mean (geo mean) and geometric coefficient of variation (GCV%)).

$C_{max}$ ,  $T_{max}$ ,  $AUC_{last}$ ,  $C_{max}/D$  and  $AUC_{last}/D$  will be calculated for all subjects with evaluable concentration-time profiles. The terminal elimination rate constant ( $\lambda_z$ ) and parameters requiring  $\lambda_z$  for calculation ( $AUC_{inf}$ ,  $AUC_{inf}/D$ ,  $t_{1/2}$ ,  $CL_z$  and  $V_z$ ) will only be reported when at least 3 points on the terminal elimination phase (excluding  $C_{max}$ ) can be fit via log-linear regression to a line with an adjusted  $R^2$  value of  $\geq 0.9$ .

In cases where  $AUC_{inf}$  can be calculated, only values with extrapolated areas  $\leq 20\%$  will be included in summary tables and statistics. All  $AUC_{inf}$  values will be reported in the listings, but values with extrapolated areas  $> 20\%$  will be flagged and footnoted as not included in the summary statistics due to the large percentage of extrapolated area.

Additional PK analysis (population PK/PD modeling or exposure response analysis) may also be conducted and will be documented separately if done.

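### Post-dose below-quantitation values are dropped from concentration summaries, so partly-BLQ time points read high; the SAP sets no rule for these summaries, and its NCA rule conflicts with the protocol's

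*Protocol*

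**What the plan says.** Protocol 9.5.3 treats two kinds of sample alike in PK and PD tabulations: those that could not be obtained or analysed, and those reported as BLQ. Both "will be ignored and not replaced by zero at any time point except the pre-first dose baseline for PK". A limit follows: "Descriptive statistics of concentrations or biomarkers at specific time points will be calculated only when at least" half of the individuals have values in the validated range. The count for this half rule "will be based on the total number of samples intended to be drawn for that time point", so BLQ and missing samples both count against reporting. For steady state there is a fallback: "If trough concentrations cannot be reported because they are BLQ, attainment of steady state will be assessed from a population PK model".

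For PK parameters the same section says: "Only concentration values within the validated concentration range and actual sampling times will be used for the calculation of pharmacokinetic parameters".

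SAP 7.12.2 covers BLQ in two settings. "For listings, BLQ will be reported as" `< LLQ`, and "For NCA, BLQ concentrations will be set to 0". It defines missing data separately, as no sample or no valid bioanalytical result. SAP 9.10.1 then requires concentrations to be "listed by subject and summarized in tables with standard descriptive statistics by analyte", part, dose level, cycle and time point. It states no BLQ rule for these summaries and does not carry over the half rule.

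**The concern.** A sample that was never drawn carries no information about the concentration. A BLQ result does: the value lies below the limit. Dropping it removes observations only from the bottom of the distribution, so every mean, median and geometric mean computed on the rest is shifted upward. The half rule decides whether a summary appears. It does not correct one that does.

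PK is a secondary objective in every part. Part A runs from 0.003 to 1 mg/kg (Protocol 6.2), a 333-fold range (1/0.003). Any BLQ values would be expected to gather in the lower dose columns and at late sampling times. Those columns would then look higher and flatter than they are beside higher doses with no BLQ values.

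The SAP leaves the programmer with either the protocol's drop rule or no rule. On NCA the two documents give different instructions for the same value.

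**Working it through.** **Inputs.** The rules are those set out above. Part A enrolled 27 subjects over six dose levels (Protocol 5.1), an average of 27/6 = 4.5 per level. The documents state no quantitation limit (LLOQ), BLQ share or between-subject CV, so there is no plan figure to reproduce and the size rests on assumptions: lognormal concentrations, CV 30-100%, BLQ share p of 10-50%.

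**Formulas.** With σ = √ln(1+CV²) and z = Φ⁻¹(p), each statistic relative to its true value is:

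- mean, BLQ dropped: Φ(σ−z)/(1−p)
- median, BLQ dropped: exp(σ·Φ⁻¹((1+p)/2))
- mean, BLQ set to 0: Φ(σ−z)
- mean, BLQ set to LLOQ/2: Φ(σ−z) + (p/2)·exp(σz − σ²/2)

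Example, CV 50% and p = 0.5: σ = √ln 1.25 = 0.472, z = 0, Φ(0.472) = 0.682, and 0.682/0.5 = 1.363 to three decimals.

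**Results (CV 30% / 50% / 100%).**

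| BLQ share | mean, dropped | median, dropped | mean, zero | mean, LLOQ/2 |
|---|---|---|---|---|
| 10% | 1.047 / 1.067 / 1.092 | 1.038 / 1.061 / 1.110 | 0.942 / 0.960 / 0.983 | 0.975 / 0.985 / 0.995 |
| 25% | 1.111 / 1.166 / 1.245 | 1.098 / 1.162 / 1.304 | 0.833 / 0.874 / 0.934 | 0.932 / 0.956 / 0.985 |
| 33% | 1.148 / 1.225 / 1.345 | 1.135 / 1.226 / 1.431 | 0.766 / 0.817 / 0.897 | 0.906 / 0.938 / 0.979 |
| 50% | 1.231 / 1.363 / 1.595 | 1.219 / 1.375 / 1.753 | 0.615 / 0.682 / 0.797 | 0.855 / 0.905 / 0.974 |

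The geometric mean with BLQ dropped, at 50% BLQ, is 1.264 / 1.458 / 1.943 of its true value.

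**What the half rule does.** With no missing samples, a summary needs 2 of 3 or 3 of 6 quantifiable values. The binomial chance that it is reported is:

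| Underlying BLQ share | n = 3 | n = 6 |
|---|---|---|
| 33% | 0.741 | 0.900 |
| 50% | 0.500 | 0.656 |
| 75% | 0.156 | 0.169 |

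So the rule suppresses most summaries in which BLQ dominates. Among those still reported the bias is unchanged. In 200,000 simulated cohorts at 50% BLQ and CV 50%, the reported mean averaged 1.364 (n = 3) and 1.363 (n = 6) of the truth, against 1.363 without the rule. The retained values come from the same truncated distribution however many there are.

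**Bound in one data set.** The mean with BLQ dropped, divided by the mean with BLQ as zero, is n/k, where k is the number quantifiable. In a reported summary this is at most 3/2 = 1.5 for n = 3 and 6/3 = 2.0 for n = 6.

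**NCA rules side by side.** Under Protocol 9.5.3 a BLQ value does not enter a parameter calculation; under SAP 7.12.2 it enters as zero. SAP 8.2.1 ends AUClast at the last quantifiable concentration, so trailing BLQ values do not affect it. A BLQ value between quantifiable ones is handled differently by the two rules.

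**The case against.** Several counterpoints have force.

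- **Dose selection.** A reader might infer that biased troughs distorted the recommended Phase 2 dose or the choice between q3w and q6w. The documents do not support this. Protocol 6.1.1 already records 0.3 mg/kg q3w for Parts A and B. SAP 3.2.4.1 names target engagement as the pharmacodynamic marker on which selection was based, and the q6w rationale in Protocol 1.4.2.2 also rests on target engagement. PK is a supporting input (Protocol 6.2.1 and 6.6). Parts F and H never opened (SAP 4), and the SAP's description of Part C omits C64.
- **Steady state.** A reader might infer that this comparison is left unprotected. Troughs that cannot be reported go to a population PK model. That fallback does not reach a time point that is partly BLQ but passes the half rule.
- **Two conventions.** Dropping BLQ in tables and zeroing it in NCA is not a contradiction in itself, because the two analyses serve different purposes. The genuine conflict is between the protocol's and the SAP's rules for parameter calculation.
- **Size.** Cohorts are small. With 3 subjects and no missing samples, at most 1 of 3 can be BLQ in a reported summary. The standard error of a mean at CV 50-100% is 29-58% for n = 3 and 20-41% for n = 6 (CV/√n), comparable with the bias or larger. This limits what any one cell can show, but the bias always runs upward and does not average out.
- **Visibility.** n is tabulated, BLQ values are listed and individual profiles are plotted, so a careful reader could detect the problem. The summary table itself would not show whether a reduced n reflects BLQ or lost samples.

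**Conclusion.** The point stands as a minor reporting correction. The drop rule is written into the protocol, the SAP does not replace it for concentration summaries, and any summary reported with some BLQ values is biased upward. Under lognormal concentrations with CV 30-100%, the mean is inflated by about 15-35% at 33% BLQ and 23-60% at 50% BLQ. The direction follows from the rule; the size depends wholly on a BLQ rate and CV that the documents do not give. Whether low-dose or late samples are in fact often BLQ cannot be settled from the documents, though the protocol does anticipate BLQ troughs.

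What is affected is the description of low-dose and late-time concentrations and the comparison across doses. Separately, Protocol 9.5.3 and SAP 7.12.2 conflict on BLQ in NCA and need to be reconciled.

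**What to change.** Amend SAP 7.12.2 as follows.

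- For concentration summaries, keep post-dose BLQ samples in n and show the number and percent BLQ at each time point.
- Compute the median and quartiles with BLQ ranked below the LLOQ, printed as `< LLQ` where they fall there. Include the case where exactly half are BLQ: with 3 of 6, the usual median would average a BLQ rank with a measured value.
- Carry over the half rule for means, footnote any mean with BLQ values present, and name the method: a substitution such as LLOQ/2, or a censored-data estimate. LLOQ/2 gives about 0.86-0.97 of the true mean at 50% BLQ, so it is an improvement but not exact. Zero is a poor choice: it gives 0.62-0.80 there and makes the geometric mean zero or undefined.
- State one BLQ rule for NCA that reconciles Protocol 9.5.3 with SAP 7.12.2.

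The cost is a few sentences, a little table programming and a substitution value in some means. No data collection changes.
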